3.2. Inclusion Criteria

Potential subjects must satisfy all of the following criteria to be enrolled in the study:

Inclusion Criteria after Screening

1. The subject will have completed the pre-screening Classification questionnaire.
2. Subject must have a working cell phone capable of sending and receiving text messages.
3. The subject must read, understand, and sign the STATEMENT OF INFORMED CONSENT and receive a fully executed copy of the form.
4. Appear able and willing to adhere to the instructions set forth in this clinical protocol
5. Between 18 and 42 (inclusive) years of age at the time of screening
6. Be a current soft contact lens wearer in both eyes with a minimum of 5 days/week wear time over the last 1 month by self-report OR be a full time spectacle wearer (7 days/ week) without contact lens wear over the last 6 months
7. Subjects must be willing to adhere to spectacle-only refractive correction for approximately 1 week

Inclusion Criteria after Baseline

8. Subjects must possess a functional / usable pair of spectacles with which they can achieve 20/25 Snellen visual acuity or better at distance and near, and bring them to the visit
9. The subject's vertex corrected spherical distance refraction must be in the range (+/-0.25 D) of -2.00 D to -6.00 D (inclusive) in each eye
10. The subject's vertex corrected refractive cylinder must be equal or less than -0.75 diopters in each eye
11. Contact lens wearers must have spherical best corrected visual acuity of 20/25 or better in each eye.
12. Snellen visual acuity at distance and near must be within 1 line between subject's own spectacle and the manifest refraction, distance and near, OD & OS.

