6. STUDY INTERVENTION

6.1. Identity of Test Articles

The control will be the subject's own spectacle.

The following contact lens will be used in this study:

Table 2: Test Lens

| | Test 1 |
|--------------------------------------|---|
| Name | ACUVUE OASYS®1-Day with HydraLuxe™ Technology |
| Manufacturer | JJVC |
| Lens Material | Senofilcon A |
| Nominal Base Curve @ 22 °C | 8.5 |
| Nominal Diameter @ 22 °C | 14.3 |
| Nominal Distance Powers (D) | -2.00 to -6.00 (0.25 steps) |
| Nominal Cylinder Powers (D) and Axes | N/A |
| Nominal ADD Powers (D) | N/A |
| Center Thickness (Optional) | 0.085 |
| Oxygen Permeability (Dk) | 103.0 |

| Test 1 | |
|--|--|
| Wear Schedule in Current Study | Daily Disposable |
| Replacement Frequency | Daily |
| Packaging Form (vial, blister, etc.) | Blister |
| Other distinguishing items (e.g., dye, packaging solution, optical design, etc.) | JJVC marketed and FDA approved production lenses |

In this study, each of 40 subjects will be fit bilaterally in daily disposably modality for up to 8 days ($40 \times 2 \times 8$). Approximately 640 contact lenses will be used in this study.

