| | | Note: if lens fit is unacceptable subject will be discontinued from the study. | |
| 1.16 | Cover test | Perform unilateral cover test with correction, distance and near to rule out strabismus | |
| 1.17 | Global Stereo | Perform global stereo testing at near to confirm binocularity. Using polarized glasses and a Randot SO-002 Stereoptical Book (or similar), presence of random-dot stereopsis at 250 second of arc will be tested with correction. | |
| 1.18 | Lens Removal and Storage (if applicable) | If present, the lenses will be removed by the subject and stored in appropriate solution or discarded if appropriate. | |
| 1.19 | Spectacle corrected visual acuity (if applicable) | For subjects that have just removed their contact lens: Record the distance and near LogMAR visual acuity (OD, OS) to the nearest letter. | |
| 1.20 | Keratometry | Record the keratometry readings OD and OS in diopters. | |
| 1.21 | Subjective Best Sphere Refraction (if interventional arm) | Complete subjective Best Sphere refraction and record the resultant Snellen distance visual acuity (OD, OS) to the nearest letter. | |
| 1.22 | Subjective Spherocylindrical Refraction | Complete subjective spherocylindrical refraction and record the Snellen resultant distance and near visual acuity (OD, OS) to the nearest letter. Near (40 centimeters): • Early Treatment Diabetic Retinopathy Study (ETDRS) 2000 Series (charts 1, 2). | |
| 1.23 | Negative relative accommodation / Positive relative accommodation (NRA/PRA) | Perform NRA/PRA in phoropter. NRA should be +1.75D to +3.00D (inclusive). PRA should be \leq -1.75D. If found to be outside of these values, the subject will be discontinued at this time. | |
| 1.24 | Slit Lamp Biomicroscopy | FDA Slit Lamp Classification Scale will be used to grade the findings and determine eligibility. If any of these slit lamp findings are grade 3 or higher, the subject may not continue at this time, but may return up to one additional time | |

| Visit 1: Baseline | | |
|-------------------|-------------------------------------|---|
| Step | Procedure | Details |
| | | to determine eligibility at the investigator's discretion. If discontinued a final examination must be completed. |
| 1.25 | Eye Rinse | If the clearance if dye needs to be expedited, the study investigator or technician will rinse the subject's eyes thoroughly with a study provided solution. |

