| 1.26 | Spectacle corrected Visual Acuity | 
Record the distance and near Snellen visual acuity (OD, OS) to the nearest letter. Subjects must read the smallest line until at least 50% of the letters are read incorrectly.
 
Near (40 centimeters):
 
 • Early Treatment Diabetic Retinopathy Study (ETDRS) 2000 Series (charts 1, 2). 
Snellen visual acuity at distance and near must be within 1 line between subject's own spectacle and the manifest refraction, distance and near, OD & OS to continue.
 |
| 1.27 | Eligibility after Baseline | 
All responses to Inclusion Criteria questions must be answered "yes" and all responses to Exclusion Criteria questions must be answered "no" for the subject to be considered eligible.
 
If a subject is deemed to be ineligible after baseline, proceed to Final Evaluation and complete all forms.
 |
| 1.28 | Randomization (if applicable) | If a subject is enrolled into the interventional arm, they will be randomized per the randomization scheme. |
| 1.29 | Treatment Selection (if applicable) | Assign the treatment based on the randomization scheme. Subjects assigned spectacle wear will continue to step 1.30. Subjects assigned contact lens wear will continue to Step 1.32 |
| 1.30 | SMS text message set up | Text message program will be set up and subject will be instructed on use. They will provide the average time they stop using their glasses/contact lenses each evening and the text message will be set to be sent 30 minutes prior to that time. |
| 1.31 | Subject instruction | The subjects will be scheduled for Visit 2 in |

| Visit 1: Baseline | | |
|-------------------|-----------|---|
| Step | Procedure | Details |
| | | 6-8 days and will present after at least 6 hours of spectacle wear on the day of the visit. |

| Visit 1: Treatment 1 (Study lens fitting) | | |
|---|--|---|
| Step | Procedure | Details |
| 1.32 | Lens Insertion | Select the contact lens power based on subjective best sphere refraction. The subject inserts the study lenses. Record the time of lens insertion. Check for lens damage under the slit lamp before proceeding with lens settling. Replace damaged lenses if applicable. |
| 1.33 | Lens Settling | Allow the study lenses to settle for a minimum of 5 minutes. |

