| 1.34 | Subjective Best Sphere Over Refraction | Perform subjective best sphere refraction over the study lenses and record the best corrected Snellen distance visual acuity to the nearest letter (OD, OS). |
| 1.35 | Lens Power Modification | Adjust the lens power if the subject's best sphere over-refraction is not plano. For each power modification, repeat steps (1.32-1.34). Up to one power modification is allowed. |
| 1.36 | Subject Reported Ocular Symptoms | Subjects will respond to a verbal open-ended symptoms questionnaire. |
| 1.37 | Subjective Lens Fit Assessment | Evaluate overall lens fit acceptance (acceptable or unacceptable) based on centration, movement and other fitting characteristics. An unacceptable fit is deemed by one of the following criteria: 
 • limbal exposure at primary gaze or with extreme eye movement • edge lift • excessive movement in primary and up gaze • insufficient movement in all three of the following conditions: primary gaze, up gaze, and Josephson push up 
Note: if lens fit is unacceptable subject will be discontinued from the study.
 |

| Visit 1: Treatment 1 (Study lens fitting) | | |
|---|--------------------------------------|--|
| Step | Procedure | Details |
| 1.38 | Contact Lens corrected Visual Acuity | Perform monocular distance and near ETDRS LogMAR visual acuity test, OD & OS |
| 1.39 | Exit Snellen Visual Acuity | Record the Snellen visual acuity, distance and near, OD & OS. Subjects must read the smallest line until at least 50% of the letters are read incorrectly. |
| 1.40 | Continuance | 
For the subject to continue in the study, they must meet all three of the following criteria:
 
 • Snellen visual acuity is 20/25 or better, distance and near (OD, OS) • The lens fit is acceptable OD and OS • Investigator approval 
If the Investigator does not approve the dispensing of the first study lens, then the study is terminated for that subject.
 |

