- Water Content: 38%
- Oxygen Permeability:

| VALUE | METHOD |
|---|---|
| 122×10^{-11} (cm ² /sec) (ml O ₂ /ml x mm Hg) at 35°C | Fatt (boundary corrected, non-edge corrected) |
| 103×10^{-11} (cm ² /sec) (ml O ₂ /ml x mm Hg) at 35°C | Fatt (boundary corrected, edge corrected) |

Lens Parameters:

- Diameter Range: 12.0 mm to 15.0 mm
- Center Thickness: varies with power
- Base Curve Range: 7.85 mm to 10.00 mm
- Spherical Power Range: -20.00D to +20.00D
- Cylinder Power Range: 0.25D to -10.00D
- Axis Range: 2.5° to 180°

AVAILABLE LENS PARAMETERS

ACUVUE OASYS® Brand 1-Day with HydraLuxe™ Technology are hemispherical shells of the following dimensions:

Diameter:

14.3 mm

Center Thickness:

0.085 mm to 0.221 mm (varies with power)

Base Curve:

8.5 mm, 9.0 mm

Powers:

-0.50D to -6.00D (in 0.25D increments)

-6.50D to -12.00D (in 0.50D increments)

+0.50D to +6.00D (in 0.25D increments)

+6.50D to +8.00D (in 0.50D increments)

ACUVUE OASYS® Brand 1-Day with HydraLuxe™ Technology for ASTIGMATISM are hemitoric shells of the following dimensions:

Diameter:

14.3 mm

Center Thickness:

0.075 mm to 0.172 mm (varies with power)

Base Curve:

8.5 mm

Powers:

+0.00D to -6.00D (in 0.25D increments)

Cylinders: -0.75D, -1.25D, -1.75D, -2.25D*

Axis: 10° to 180° in 10° increments

*-2.25D cylinder is available in 10°, 20°, 70°, 80°, 90°, 100°, 110°, 160°, 170°, 180° axes only.

+0.25D to +4.00D (in 0.25D increments)

[figure not shown]
-6.50D to -9.00D (in 0.50D increments)

Cylinders: -0.75D, -1.25D, -1.75D

Axis: 10°, 20°, 70°, 80°, 90°, 100°, 110°, 160°, 170°, 180°

TRANSMITTANCE CURVES

ACUVUE OASYS® 1-Day with HydraLuxe™ Technology (senofilcon A)
Visibility Tinted with UV Blocker vs. 24 yr. old human cornea and 25 yr. old
human crystalline lens.

* The data was obtained from measurements taken through the central 3-5 mm portion for the thinnest marketed lens (-9.00D lens, 0.075 mm center thickness).

¹Lerman, S., Radiant Energy and the Eye, MacMillan, New York, 1980, p. 58, figure 2-21

²Waxler, M., Hitchins, V.M., Optical Radiation and Visual Health, CRC Press, Boca Raton, Florida, 1986, p. 19, figure 5

WARNING: UV absorbing contact lenses are NOT substitutes for protective UV absorbing eyewear, such as UV absorbing goggles or sunglasses because they do not completely cover the eye and surrounding area. The patient should continue to use UV absorbing eyewear as directed.

ACTIONS

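### Inclusion criterion 9 and the Table 2 lens powers do not match, and no eligibility rule before randomisation checks best sphere against those powers

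*Combined protocol and SAP*

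**What the plan says.** **Eligibility.** Criterion 9, in section 3.2 and repeated in the synopsis, requires that the vertex-corrected "spherical distance refraction must be in the range (+/-0.25 D) of -2.00 D to -6.00 D (inclusive) in each eye". Criterion 10 adds that the "vertex corrected refractive cylinder must be equal or less than -0.75 diopters in each eye". Criterion 11 requires contact lens wearers to reach 20/25 with their best spherical correction.

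**Lenses.** Table 2 in section 6.1 lists one spherical lens, with powers from minus "2.00 to -6.00 (0.25 steps") and no cylinder. The package insert in Appendix C gives the marketed minus powers near these limits as minus "0.50D to -6.00D (in 0.25D increments") and then minus "6.50D to -12.00D (in 0.50D increments"). So -1.75 D is marketed but not listed for the study, and -6.25 D is not made.

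**Order of steps at Visit 1 (section 7.2).**
- Step 1.21, interventional arm: "Complete subjective Best Sphere refraction and record the resultant Snellen distance visual acuity (OD, OS) to the nearest letter".
- Step 1.27: eligibility is confirmed.
- Step 1.28: randomisation.
- Step 1.32, for those given the lens first: "Select the contact lens power based on subjective best sphere refraction".
- Step 1.35: "Adjust the lens power if the subject's best sphere over-refraction is not plano", with at most one modification.
- Step 1.40: to continue, the subject needs 20/25 or better with the lens, an acceptable fit and investigator approval.

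Subjects given spectacles first reach the same lens selection and continuance steps at Visit 3 (steps 3.13 to 3.24).

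**The concern.** The admitted refraction range is wider than the listed lens range. The quantity that sets lens power is known before randomisation, yet no eligibility rule uses it. Criterion 11 does not fill the gap, because it tests acuity with the best sphere and not with a lens from Table 2.

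Two things are at stake in the interventional arm.

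- **Losses after randomisation that differ by sequence.** A lens-first subject who fails step 1.40 leaves at Visit 1, before any tear-film measurement. A spectacle-first subject with the same eyes fails at step 3.24, after giving period 1 spectacle data. Section 14.7 uses first-period data for the comparison with habitual spectacle wearers, so such eyes could remain in the first-period spectacle data and be absent from the first-period lens data.
- **Residual refractive error in one period only.** A subject who passes 20/25 may wear a lens that is off by the residual for the lens week. In the spectacle week, criterion 12 has already held the spectacles to within one line of the manifest refraction. The residual then goes with lens type in the comfort and digital-device symptom data.

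**Working it through.** **The plan's own figure.** The only computed figure in the plan is the 86% power in section 14.2. It is not in dispute, but it bounds the cost of lost subjects. Inputs: variance 34, same-eye ICC 0.5, difference 2 seconds, 80 eyes, two-sided 0.05. The within-eye period difference has variance 2 x 34 x (1 - 0.5) = 34. The subject-level ICC of 0.3 applies equally within and across periods, so it cancels from the covariance between the two eyes' differences. SE = sqrt(34/80) = 0.652, and 2/0.652 = 3.07. Power is 86.6% (normal), 85.8% (t, 78 df) or 84.8% (t, 38 df), so 86% reproduces. With fewer completers and no replacement, the normal approximation gives 84.9% at 38, 82.9% at 36, 80.7% at 34 and 75.7% at 30.

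**Ranges side by side.** Admitted by criterion 9: -2.00 + 0.25 = -1.75 D to -6.00 - 0.25 = -6.25 D, which is 19 quarter-dioptre steps. Listed in Table 2: -2.00 to -6.00 D, which is 17 powers.

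**Reading A: criterion 9 means best sphere.** Two of the 19 steps, -1.75 and -6.25 D, lie outside the listed powers, each by 0.25 D. Cylinder adds nothing.

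**Reading B: criterion 9 means the sphere component.** Assumptions: best sphere = sphere + cylinder/2 (the documents give no formula), and criterion 10 admits cylinder of 0, -0.25, -0.50 or -0.75 D. Admitted combinations: 19 x 4 = 76. Those with best sphere outside Table 2 are:

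| Sphere / cylinder (D) | Best sphere (D) | Distance from nearest listed power (D) |
|---|---|---|
| -6.25 / 0 | -6.25 | 0.25 |
| -6.25 / -0.25 | -6.375 | 0.375 |
| -6.25 / -0.50 | -6.50 | 0.50 |
| -6.25 / -0.75 | -6.625 | 0.625 |
| -6.00 / -0.25 | -6.125 | 0.125 |
| -6.00 / -0.50 | -6.25 | 0.25 |
| -6.00 / -0.75 | -6.375 | 0.375 |
| -5.75 / -0.75 | -6.125 | 0.125 |
| -1.75 / 0 | -1.75 | 0.25 |
| -1.75 / -0.25 | -1.875 | 0.125 |

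That is 10 of 76 outside the listed range: 7 by at least 0.25 D, of which 4 exceed 0.25 D. The three at 0.125 D are no worse than rounding inside the range, since lenses come in 0.25 D steps.

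**Deleting the tolerance only.** 17 x 4 = 68 combinations remain. The four with sphere -6.00 or -5.75 D in the table stay outside, two of them by at least 0.25 D, with a maximum of 0.375 D.

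**Adding -1.75 and -6.50 D lenses.** A best sphere of -6.25 D lies 0.25 D from both -6.00 and -6.50 D, so it still cannot reach plano.

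**The case against.** A reader might infer four stronger things. The documents support none of them.

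- **That the listed lenses cannot correct these eyes.** Plano is not a condition for dispensing. Step 1.35 allows one power change, and continuance rests on 20/25, fit and investigator approval. Nothing in the documents shows that a residual of 0.25 to 0.625 D fails 20/25. At the low end the excess is at most 0.25 D of minus, in subjects who have passed the PRA test at step 1.23.
- **That the mismatch comes to light only after randomisation.** Best sphere is recorded at step 1.21, before randomisation. What is missing is a rule that acts on it.
- **That 10 of 76 is a share of patients.** It counts grid cells of equal weight. The refraction distribution is not given.
- **That the primary result is biased.** NIBUT/NIKBUT times the break-up of rings reflected from the tear film, and nothing in the plan links it to residual refractive error.

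The strongest remaining defence is that the study already provides for such losses. Poor vision at dispensing is a listed withdrawal reason, discontinued subjects are replaced (section 8.2), and 46 are randomised so that 40 complete (Table 1). The study is an exploratory pilot, and the comfort and symptom endpoints are analysed descriptively. This stands as to power: a few losses cost little. It does not answer the sequence-dependent timing of any loss, and it leaves sites with an over-refraction instruction that the listed powers cannot meet for some eligible eyes.

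**Conclusion.** The point holds as a mismatch between criterion 9 and Table 2 that no eligibility step before randomisation resolves. The size is 0.25 D at each end if criterion 9 means best sphere. It is up to 0.625 D at the minus end if it means the sphere component. The larger figure depends on that reading, on best sphere being sphere plus half the cylinder, and on reading criterion 10 as 0 to -0.75 D, although its wording is ambiguous in sign.

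How many subjects are affected is unknown. Both eyes must meet the criteria, so one eye at the edge is enough to affect a subject. Any harm lies in avoidable losses after randomisation, at Visit 1 or Visit 3 according to sequence, and in residual error confined to the lens period for exploratory comfort and symptom endpoints. The stated power and the primary NIBUT comparison are not called into question. The change is still worth making, because it uses a measurement already taken.

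**What to change.** Reconcile criteria 9 and 10 with Table 2 before randomisation, in section 3.2 and the synopsis:

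1. Define the refraction meant in criterion 9 (best sphere or sphere component), and state the cylinder limit in criterion 10 without ambiguity of sign.
2. For the interventional arm, require at step 1.27 that the vertex-corrected best sphere from step 1.21 lie within the Table 2 power range in each eye.

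Under either reading this leaves no eligible interventional-arm eye with a best sphere outside the listed range, and it needs no new procedure. Deleting the tolerance alone is not enough under the sphere-component reading, since 4 of 68 combinations stay outside. Adding -1.75 and -6.50 D lenses does not solve it either, because of the -6.25 D best sphere.

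The cost is a short amendment, a few extra screen failures at the edges of the range (the number cannot be estimated from the documents), and a refractive criterion slightly different from that of the observational arm. Since that arm serves as a reference group, the difference should be stated when the two are compared.

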3.3. Exclusion Criteria

Potential subjects who meet any of the following criteria will be excluded from participating in the study:

Exclusion Criteria after Screening:

1. Currently pregnant or lactating, by self-report
2. Any ocular or systemic allergies, disease or use of medication which may interfere with contact lens wear and/or participation in the study (at the discretion of the investigator).
3. Any active ocular abnormalities/conditions that may interfere with contact lens wear and/or participation in the study (at the discretion of the investigator).
4. Any corneal distortion resulting from previous hard or rigid gas permeable contact lens wear

5. Habitual contact lens wear modality as extended wear (≥ 1 night per month of extended wear)
6. Habitual contact lens is rigid gas permeable, toric, monovision or multi-focal
7. Habitual spectacle contains an add power, photochromic or tint.
8. Any previous, or planned (during the course of the study) ocular surgery (e.g., radial keratotomy, PRK, LASIK, etc.)
9. Participation in any contact lens or lens care product clinical trial within 2 weeks prior to study enrollment.
10. Employee or employee's immediate family member of clinical site (e.g., Investigator, Coordinator, Technician)
11. Current habitual use of Restasis, Xiidra, ocular steroids, or any medication (RX or OTC) that may interfere with contact lens wear and/or participation in the study (at the discretion of the investigator)

Exclusion Criteria after Baseline

12. Any ocular allergies, infections or other ocular abnormalities that are known to interfere with contact lens wear and/or participation in the study. This may include, but not be limited to entropion, ectropion, extrusions, chalazia, recurrent styes, glaucoma, history of recurrent corneal erosions, aphakia, or corneal distortion
13. Any Grade 3 or greater biomicroscopy findings (this includes, corneal edema, corneal staining, corneal vascularization, conjunctival injection, tarsal abnormalities, bulbar injection) on the FDA classification scale [REDACTED]
14. Accommodative/binocular dysfunction, determined by study procedures.

3.4. Enrollment Strategy

Study subjects will be recruited from the Institution/clinical site's subject database and/or utilizing Independent Ethics Committee (IEC) or Institutional Review Board (IRB) approved materials.

The clinical site will administer a pre-screening on potential subjects before they attend the initial study visit utilizing IEC/IRB approved recruitment materials.

4. STUDY DESIGN AND RATIONALE

4.1. Description of Study Design

This is two-arm study. There will be an observational arm and an interventional arm.

In the observational arm, habitual spectacle wearers will all continue to use their habitual optical correction and undergo ocular evaluations and questionnaires at 2 separate study visits: baseline and 1-week. Since the nature of this arm is observational, it will be non-controlled, non-randomized, and unmasked.

In the interventional arm, habitual contact lens wearers who own spectacles will undergo a bilateral, 1-week dispensing, randomized, controlled, unmasked, 2×2 cross-over study with a 1-week washout between periods in which subjects will wear their habitual contact lens.

Each subject will be bilaterally fitted with the one test article and crossed with their own spectacle in 2 periods.

